GGT	gamma-glutamyl transferase
GM	geometric mean
H	hours
HAART	Highly Active Anti-Retroviral Therapy
HIV	Human Immunodeficiency Virus
HR	heart rate
IB	Investigator's Brochure
ICF	informed consent form
ICH	International Conference on Harmonisation
IMP	Investigational Medicinal Product
IEC	Independent Ethics Committee
Max	maximum
MedDRA	Medical Dictionary for Regulatory Activities
mg	milligram
Min	minimum
mL	milliliter
mmHg	millimeters of mercury
NOAEL	No Observed Adverse Effect Level
o.d.	Once Daily
PD	pharmacodynamics
PK	pharmacokinetics
PT	preferred term
PCSA	potentially clinically significant abnormalities
QTc	heart-rate-corrected QT interval (time between the start of the Q wave and the end of the T wave in the heart's electrical cycle) using Bazett's formula
R	Accumulation ratio
RTV	Ritonavir
Rx	Treatment
SAE	serious adverse event
SBP	systolic blood pressure
SD	standard deviation
SEM	standard error of the mean
SOC	system organ class
TEAE	treatment emergent adverse event
t _{lag}	interval between administration time and the sampling time preceding the first concentration above the limit of quantification
t _{1/2}	terminal half-life
t _{max}	time to peak plasma concentration
Vd/F	volume of distribution
vs.	versus

SYNOPSIS

Study n°	ABX464-005	Clinical Phase	Ib
		Type of Study	PK/Safety Study
Study title	An Open-Label Study of the Safety, Pharmacokinetics, and Pharmacodynamics of ABX464 in HIV-1 Seronegative and Seropositive Adults		
Short title	Safety study of ABX464 in HIV-1 Seronegative and Seropositive adult subjects.		
Investigators and study centers	
The study will be conducted at the Hospital Universitari Germans Trias i Pujol (Can Ruti), Badalona, Spain
 
Collaborating centre: BCN Checkpoint, Barcelona, Spain
		
Study Duration	
Recruitment period: Q4 2016 – Q2 2018
 
Overall Study period: Q4 2016 – Q1 2019
		
Investigational product			
Study Methodology	
The purpose of the ABX464-005 study is to characterize the systemic and mucosal immunological sequelae associated with exposure to ABX464 and to explore selected immunological endpoints, compartmental pharmacokinetics, and pharmacodynamics. The site will screen and enroll 12 HIV-infected subjects who will receive 150 mg ABX464 orally once daily for 28 days (Cohort 1). Following completion of this cohort a further 24 subjects will be enrolled: 12 HIV-uninfected subjects will receive 50 mg ABX464 orally once daily for 28 days (Cohort 2) and 12 HIV-infected subjects (Cohort 3) who will 50 mg ABX464 orally once daily for 84 days.
 
Following screening, eligible subjects in all cohorts will undergo a baseline visit during which blood and tissue samples will be collected. All subjects will have additional blood and tissue samples collected on Day 28 of dosing (and on Day 84 for subjects enrolled in cohort 3) and four weeks after completion of dosing (excluding cohort 2 for tissue samples). The HIV infected subjects should be receiving a stable combination antiretroviral regimen for 12 months and be fully virally suppressed (plasma viral load < 50 copies/mL) during the last 6 months prior to enrolment.
 
Dose limiting toxicity (DLT) is defined as a grade 3 or higher adverse event as defined by the Division of AIDS table for grading the severity of adult and pediatric adverse events (including signs/symptoms, lab toxicities and/or clinical events) considered by the Data Safety Monitoring Board as probably or definitely related to study treatment.
 
If more than 2 DLTs occur during the treatment period of the first four treated subjects, then the enrolment of additional subjects will be stopped. In addition, in case of a life threatening (grade 4) adverse reaction enrolment and treatment of ongoing subjects will be immediately discontinued. In both cases, enrolment will only be resumed upon the decision of the sponsor if the Data Safety Monitoring Board can conclude that the causality of the event was unrelated or unlikely related to study treatment.
		
Study Design			

Study n°	ABX464-005	Clinical Phase	Ib
		Type of Study	PK/Safety Study
Study Objectives	
Primary objective:
 
 To evaluate the distribution of ABX464 and its main metabolite (N-Glu) in various compartments in HIV-1 Seronegative and Seropositive adult subjects. 
Secondary objectives:
 
 To evaluate the safety of ABX464 administered once daily at one dose, alone in HIV-uninfected subjects and in combination with ARTs in HIV-1 infected adult subjects; To evaluate the systemic and mucosal immunological response to ABX464 in HIV-uninfected and or in HIV-infected adult subjects; To evaluate the effect of ABX464 on the HIV reservoir cells in HIV-infected adult subjects; To evaluate the effect of ABX464 on the control of the viral load and the CD4+/CD8+ in HIV-infected adult subjects; To evaluate the effect of ABX464 on the microbiome in HIV-1 Seronegative and Seropositive adult subjects; To evaluate the effect of ABX464 on the rectal transcriptome & proteome in HIV-1 Seronegative and Seropositive adult subjects. 		
Study Endpoints	
Primary endpoint:
 
Main pharmacokinetic parameters (Cmax, AUC) after first dose of ABX464 (Day 1):
 
 Cohort 1: at Day 28 and at Day 56 for plasma, PBMC and rectal tissue. Cohort 2: at Day 28 and at Day 56 for plasma and PBMC. Rectal tissue only at Day 28. Cohort 3: at Day 28, Day 84 and Day 112 for plasma, PBMC and rectal tissue. 		

Study n°	ABX464-005	Clinical Phase	Ib
Type of Study	PK/Safety Study		
Secondary endpoints:	
 ▪ Number and grade of treatment-emergent adverse events, including treatment-emergent serious adverse events, adverse events leading to investigational product discontinuation, during the study; ▪ Change in GALT HIV reservoirs in rectal tissue from Baseline to Day 28 and Day 56 in HIV-infected subjects (Cohort 1) and from Baseline to Day 28, Day 84 and Day 112 (Cohort 3); ▪ Change in total viral DNA in the reservoir cells from Baseline to Day 28 and Day 56 in HIV-infected subjects (Cohort 1) and from Baseline to Day 28, Day 84 and Day 112 (Cohort 3); ▪ Change in inflammatory markers in plasma from Baseline to Day 28 and Day 56 in subjects enrolled in Cohort 1 & 2 and to Day 28, Day 84 and Day 112 in subjects enrolled in Cohort 3; ▪ Change in immunophenotype and assessment of cell-activation markers from Baseline in PBMCs and MMC, using an 11-colours panel, including: CD3, CD8, CD4, CD45RA, CCR7, CD27, CD28, CD38, HLA-DR, PD-1, viability to Day 28 and Day 56 in subjects enrolled in Cohort 1 & 2 and to Day 28, Day 84 and Day 112 in subjects enrolled in Cohort 3; ▪ Change in HIV-1 RNA, CD4+ and CD8+ counts from Baseline to Day 28 and Day 56 in HIV-infected subjects (Cohort 1) and from Baseline to Day 28, Day 84 and Day 112 (Cohort 3); ▪ Change of rectal microbiota using taxonomic markers from Baseline to Day 28 and Day 56 in subjects enrolled in Cohort 1, change of rectal microbiota using taxonomic markers from Baseline to Day 28 in subjects enrolled in Cohort 2 and to Day 28, Day 84 and Day 112 in subjects enrolled in Cohort 3; ▪ Change in the transcriptome & proteome from Baseline to Day 28 and Day 56 in subjects enrolled in Cohort 1, change in the transcriptome & proteome from Baseline to Day 28 in Cohort 2 and to Day 28, Day 84 and Day 112 in subjects enrolled in Cohort 3. 		
Main Selection Criteria	Inclusion criteria:	Subjects will be eligible for inclusion in this study only if ALL of the following criteria apply:	
	
 • Males aged 18-65 years; • Subjects with hematological and biochemical laboratory parameters as follows and within 3 weeks of baseline: 
 • Hemoglobin > 9.0 g/dL; • Absolute neutrophil count \geq 750/mm³; • Platelets \geq 100,000/mm³; • Total serum creatinine \leq 1.3 x ULN (upper limit of normal); • Creatinine clearance > 50 mL/min by the Cockcroft-Gault equation within 60 days of entry; • Total serum bilirubin < 1.5 x ULN; • Alkaline phosphatase, AST (SGOT) and ALT (SGPT) < 1.5 x ULN; • Serum lipase less than or equal to 2.0 x ULN; • Subjects should be able and willing to comply with study visits and procedures as per protocol; • Subjects should understand, sign and date the written voluntary informed consent form at the screening visit prior to any protocol-specific procedures being performed; • Subjects must agree to use in addition to the condom, a second highly effective method (one for the subject and one for the partner) of contraception (defined as per the CTG Guidance) during the study and for 3 months after end of study or early termination. 		

Study n°	ABX464-005	Clinical Phase	Ib
Type of Study	PK/Safety Study		
	
For HIV positive Subjects
 
 Subjects with a positive HIV-1 serology at any time before the study entry; Subjects treated for at least 12 months prior to screening with Dolutegravir or Raltegravir combined with either Tenofovir + Emtricitabine (TDF/FTC) or Abacavir + Lamivudine (ABC/3TC); Subjects with HIV plasma viral load \leq 50 copies/mL during the 6 months prior to screening with a maximum of 2 blips \leq 1000 copies during this period; Subjects' CD4+ T cells count \geq 250 cells per mm³ at any time since diagnosis; Subjects with CD4+ T cells count \geq 600 cells per mm³ at screening. 		
Exclusion criteria	
The following criteria should be checked at the time of screening. If ANY exclusion criterion applies, the individual will not be included in the study:
 
 History of allergic disease, anaphylaxis or reactions likely to be triggered or exacerbated by any component of investigational products; Acute or chronic infectious disease other than HIV infection (include but not limited to viral hepatitis such as hepatitis B, hepatitis C, active tuberculosis, active syphilis [i.e. currently treated]). Acute, chronic or history of clinically relevant pulmonary, cardiovascular, gastrointestinal, hepatic, pancreatic or renal functional abnormality, encephalopathy, neuropathy or unstable CNS pathology, angina or cardiac arrhythmias, or any other clinically significant medical problems as determined by physical examination and/or laboratory screening tests and/or medical history; Severe hepatic impairment; Acute, chronic or history of immunodeficiency or autoimmune disease other than HIV infection; Unstable asthma (defined as sudden acute attacks occurring in less than three hours without an obvious trigger, hospitalization for asthma in the last two years); food or wine induced asthma; History of malignancy unless there has been surgical excision that is considered to have achieved cure; Active malignancy that may require chemotherapy or radiation therapy; Seizure disorder or any history of prior seizure; Serious illness requiring systemic treatment and/or hospitalization within 7 days prior to baseline; Active drug or alcohol abuse or dependence; Subjects reporting a use of a prohibited medication; History of significant gastrointestinal bleeding in the opinion of the investigator; Abnormalities of the colorectal mucosa, or significant symptom(s), which in the opinion of the clinician represents a contraindication to protocol-required biopsies (including but not limited to presence of any unresolved injury, infectious or inflammatory condition); Any condition, which in the opinion of the investigator, could compromise the subject's safety or adherence to the study protocol. 		
Medications	
Mandatory treatment:
 
 HIV infected Subjects must be on a stable antiretroviral regimen for 12 months and have a plasma viral load of $<$ 50 copies/mL for at least 6 months prior to enrolment into the study and be willing to continue their antiretroviral regimen for the duration of the ABX464-005 study 
All subjects enrolled in Cohort 1 will receive ABX464 150 mg dose from Day 1 to Day 28 while subjects enrolled in Cohorts 2&3 will receive ABX464 50 mg dose respectively from Day 0 to Day 28 and from Day 0 to Day 84.
		

Study n°	ABX464-005	Clinical Phase	Ib
		Type of Study	PK/Safety Study
Prohibited prior or Concomitant treatments:			Following medications are prohibited potentially prior to baseline and during the course of the study.

 • Medications prohibited within 3 months prior to baseline and during the whole course of the study 
 ◦ Immunomodulators or immunosuppressive drugs (such as IL-2, IL-7, intravenous immunoglobulin-IVIG, IFNa, or Imiquimod); ◦ Any investigational or non-registered product. • Medications prohibited within 1 month prior to baseline and during the whole course of the study 
 ◦ HIV uninfected Subjects should not be taking antiretroviral pre-exposure prophylaxis (PrEP) or have completed a course of antiretroviral post exposure prophylaxis (PEP) within one month of the enrollment visit. • Medications prohibited within one week prior to baseline and during the whole course of the study. 
 ◦ Heparin, including Lovenox® (enoxaparin sodium); ◦ Warfarin; ◦ Plavix® (clopidogrel bisulfate); ◦ Any other drugs that are associated with increased likelihood of bleeding following mucosal biopsy (e.g., daily high dose aspirin (> than 81 mg), NSAIDs, or Pradaxa®); ◦ Rectally administered medications (including over-the-counter products); ◦ Multiple dose dexamethasone. • Medications prohibited during the whole course of the study 
 ◦ Drugs that could interact either with ABX464 should be avoided especially the CYP1A2 substrates or inducers (cf. Appendix#2). The following CYP1A2 substrates or inducers with a narrow therapeutic margin are prohibited during the whole course of the study (clozapine, theophylline, ropinirole, warfarin and methadone). 			
Premature trial discontinuation	Subject's premature trial discontinuation could occur for the following reasons:		
	
 • Investigator's decision; • An Adverse Event or an intercurrent condition that preclude continuation of treatment; 
 ◦ Specifically, an increase $\geq 2.0 \times$ ULN in liver transaminases (AST/SGOT and/or ALT/SGPT), in alkaline phosphatase or in total bilirubin should be considered a treatment discontinuation criterion. • Major protocol violation; • Subject's decision; • Withdrawal of consent. 		
Data Safety Monitoring Board (DSMB)	A Data Safety Monitoring Board with expertise and experience in the management in HIV will review the safety of the trial, every 4 patients are recruited, in order to recommend, if appropriate, the continuation of the study.		
Number of subjects planned	No formal sample size calculations were performed. 36 subjects (24 HIV infected and 12 HIV uninfected subjects) are deemed sufficient to fulfil the study objectives.		
Statistical Methods	
Safety:
 
Analysis of safety will be performed on the safety data set consisting in all subjects who received at least one dose of ABX464 in the study. The assessment of safety will be based on the frequency of adverse events (with and without regard to causality) graded according to the Division of AIDS table for grading the severity of adult and pediatric adverse events (Version 2.0 November 2014) and also, the review of individual values for clinical laboratory data, vital signs and ECG focusing on the detection of abnormal values and PCSAs [potentially clinically significant abnormalities (PCSAs) determined upon investigator
		

Study n°	ABX464-005	Clinical Phase	Ib																																													
		Type of Study	PK/Safety Study																																													
	
considerations].
 
Adverse events will be tabulated (counts and percents) by group and dose. All adverse events will be listed and the data will be tabulated by body system/organ class. Adverse event tabulations will include all treatment emergent adverse events, which will be further classified by severity, and relationship to treatment and dose level.
 
Clinical laboratory parameters, vital signs, ECG will be summarized by using descriptive statistics (n, mean, SD, SEM, median, minimum and maximum). Number of subjects with at least one abnormal values will be tabulated (counts and percents) for each parameter in summary shift tables, by group and dose.
 
Efficacy:
 
All efficacy endpoints will be summarized descriptively. Virological control, HIV reservoirs, etc. will be analyzed before versus after treatment
 
Interim analysis:
 
An interim analysis will be produced when the first 12 HIV-positive subjects (Cohort 1) reach day 56 of follow-up. The interim analysis will include the following data:
 
 • Safety and clinical parameters; • HIV-1 RNA, CD4+ and CD8+ counts; • Hematology and biochemistry parameters; • Pharmacokinetic parameters in plasma, PBMCs and rectal tissue; • Total HIV-1 DNA reservoir in PBMC and rectal tissue. 																																															
Pharmacokinetic s:	
ABX464 has a very short $t_{1/2}$ (1 to 2 h) and generally no drug could be quantified after 10h post-dose, so steady-state is virtually reached at the second administration.
 
NGlcABX464 (main ABX464 metabolite) has a $t_{1/2}$ of 90 to 110 h, meaning that steady-state is reached after 19 to 22 days of administration.
 
Pharmacokinetic parameters will be assessed in plasma, in PBMC and in rectal mucosa.
 
Intensive Pharmacokinetic runs will be conducted after the first dose of ABX464 (Day 1), after the final dose (Day 28/Day 84) and at day 56/112 for plasma, PBMC and rectal tissue (Rectal tissue only cohorts 1 and 3 at day 56). Samples will be collected according to the schedule below:
 
  
 	Day 1	Day 28 (Cohort 1&2) Day 28 & 84 (Cohort 3)	Day 35 (Cohort 1&2) Day 91 (Cohort 3)	Day 56 (Cohort 1&2) Day 112 (Cohort 3)	
   
 HIV infected Subjects	
 
 Plasma	0h, 0.5h, 1h, 1.5h, 2h, 4h, 6h and 8 hours	0h, 0.5h, 1h, 1.5h, 2h, 4h, 6h and 8 hours	Trough level	Trough level	
 
 PBMC	0h, 0.5h, 1h, 1.5h, 2h, 4h, 6h and 8 hours	0h, 0.5h, 1h, 1.5h, 2h, 4h, 6h and 8 hours	Trough level	Trough level	
 
 Rectal tissue	Rectal biopsies	Rectal biopsies		Rectal biopsies	
 
 HIV non-infected Subjects	
 
 Plasma	0h, 0.5h, 1h, 1.5h, 2h, 4h, 6h and 8 hours	0h, 0.5h, 1h, 1.5h, 2h, 4h, 6h and 8 hours	Trough level	Trough level	
 
 PBMC	0h, 0.5h, 1h, 1.5h, 2h, 4h, 6h and 8 hours	0h, 0.5h, 1h, 1.5h, 2h, 4h, 6h and 8 hours	Trough level	Trough level	
 
 Rectal tissue	Rectal biopsies	Rectal biopsies			
  
				Day 1	Day 28 (Cohort 1&2) Day 28 & 84 (Cohort 3)	Day 35 (Cohort 1&2) Day 91 (Cohort 3)	Day 56 (Cohort 1&2) Day 112 (Cohort 3)	HIV infected Subjects					Plasma	0h, 0.5h, 1h, 1.5h, 2h, 4h, 6h and 8 hours	0h, 0.5h, 1h, 1.5h, 2h, 4h, 6h and 8 hours	Trough level	Trough level	PBMC	0h, 0.5h, 1h, 1.5h, 2h, 4h, 6h and 8 hours	0h, 0.5h, 1h, 1.5h, 2h, 4h, 6h and 8 hours	Trough level	Trough level	Rectal tissue	Rectal biopsies	Rectal biopsies		Rectal biopsies	HIV non-infected Subjects					Plasma	0h, 0.5h, 1h, 1.5h, 2h, 4h, 6h and 8 hours	0h, 0.5h, 1h, 1.5h, 2h, 4h, 6h and 8 hours	Trough level	Trough level	PBMC	0h, 0.5h, 1h, 1.5h, 2h, 4h, 6h and 8 hours	0h, 0.5h, 1h, 1.5h, 2h, 4h, 6h and 8 hours	Trough level	Trough level	Rectal tissue	Rectal biopsies	Rectal biopsies		
	Day 1	Day 28 (Cohort 1&2) Day 28 & 84 (Cohort 3)	Day 35 (Cohort 1&2) Day 91 (Cohort 3)	Day 56 (Cohort 1&2) Day 112 (Cohort 3)																																												
HIV infected Subjects																																																
Plasma	0h, 0.5h, 1h, 1.5h, 2h, 4h, 6h and 8 hours	0h, 0.5h, 1h, 1.5h, 2h, 4h, 6h and 8 hours	Trough level	Trough level																																												
PBMC	0h, 0.5h, 1h, 1.5h, 2h, 4h, 6h and 8 hours	0h, 0.5h, 1h, 1.5h, 2h, 4h, 6h and 8 hours	Trough level	Trough level																																												
Rectal tissue	Rectal biopsies	Rectal biopsies		Rectal biopsies																																												
HIV non-infected Subjects																																																
Plasma	0h, 0.5h, 1h, 1.5h, 2h, 4h, 6h and 8 hours	0h, 0.5h, 1h, 1.5h, 2h, 4h, 6h and 8 hours	Trough level	Trough level																																												
PBMC	0h, 0.5h, 1h, 1.5h, 2h, 4h, 6h and 8 hours	0h, 0.5h, 1h, 1.5h, 2h, 4h, 6h and 8 hours	Trough level	Trough level																																												
Rectal tissue	Rectal biopsies	Rectal biopsies																																														
Immunological assays	
Tissue Immunological evaluation:
 
Up to 20 rectal biopsies will be collected 15 cm from the anal verge and will be used to:
 
 • Determine whether ABX464 alters gut associated lymphoid tissue (GALT) immunology; • Assess whether exposure to ABX464 alters HIV GALT reservoirs in the HIV-positive subjects or reduce the incidence or magnitude of HIV infection in rectal tissue from HIV-negative subjects. 
GALT HIV reservoirs (RNA and DNA) will be characterized using previously published techniques.
																																															

Study n°	ABX464-005	Clinical Phase	Ib
Type of Study	PK/Safety Study		
	
Ex vivo / in vitro rectal explant challenge will also be performed using previously published techniques in which rectal biopsies are challenged with high titers of HIV-1BaL and cumulative, weight adjusted HIV-1 p24 antigen is quantified in the explantsupernatant.
 
Effect on inflammation and/or activation:
 
Potential changes related to the investigational product on the inflammation and activation status of the subjects will be assessed throughout:
 
 Quantification of systemic inflammatory markers in plasma Immunophenotype and assessment of cell-activation markers in PBMCs and MMC, using an 11-colours panel, including: CD3, CD8, CD4, CD45RA, CCR7, CD27, CD28, CD38, HLA-DR, PD-1, viability. 		
Microbiome, transcriptome & proteome	
Additional studies of rectal microbiome, mucosal transcriptome and proteome will provide a comprehensive assessment of mucosal biology before and after exposure to ABX464 in HIV-1 Seronegative and Seropositive adult subjects.
		

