3.1.2. Dose limiting toxicity (DLT)

A dose limiting toxicity (DLT) is defined as a grade 3 or higher adverse event as defined by the Division of AIDS Toxicity Table for Severe Adult and Pediatric Adverse Events (including signs/symptoms, lab toxicities and/or clinical events) considered by a safety review board as probably or definitely related to study treatment. The first four subjects will be enrolled first and followed up for at least 2 weeks of treatment. If more than 2 DLTs occur of the first four treated subjects during ongoing study participation, then the enrolment of additional subjects will be stopped.

In addition, in case of a life threatening (grade 4) adverse reaction enrolment and treatment of ongoing subjects will be immediately discontinued.

In both cases, enrolment will only be resumed upon the decision of the sponsor if the Data Safety Monitoring Board can conclude that the causality of the event was unrelated or unlikely related to study treatment.

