5.4.3. Hematology and biochemistry

For hematology and biochemistry local laboratories will be used. All laboratory results and reference ranges for safety parameters must be entered in the eCRF. Each laboratory value that is outside of the institution's normal range will be identified. The investigator will be responsible for assessing the clinical significance of laboratory abnormalities. If the investigator is uncertain about the clinical significance of a laboratory abnormality, he/she will consult with the Sponsor medical monitor. The investigator should follow any clinically significant laboratory abnormalities until resolution.

Table 4 displays the clinical laboratory parameters that must be measured at every visit.

Table 4: Laboratory Tests

HEMATOLOGY		BIOCHEMISTRY
Hemoglobin		Sodium
Hematocrit		Potassium
WBC		Chloride
Neutrophils		Calcium
Lymphocytes		Phosphate
Monocytes		Glucose
Eosinophils		BUN or urea
Basophils		Creatinine
Platelet count		AST
INR		ALT
PT		Alkaline phosphatase
		Total bilirubin
		GLDH
		Total protein
		Lipase
		Albumin
		LDH
		gGT
		CRP

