8.3. Events or Outcomes Qualifying as AEs or SAEs

8.3.1. Clinical laboratory parameters

Abnormal laboratory findings (e.g., clinical chemistry, hematology) or other abnormal assessments (e.g. vital signs) that are judged by the investigator as **clinically significant** will be recorded as AEs or SAEs if they meet the definitions of sections 8.1 and 8.2 respectively. Clinically significant abnormal laboratory findings or other abnormal assessments that are detected during the study or are present at informed consent and significantly worsen during the study will be reported as AEs or SAEs. Clinically significant abnormal laboratory findings or other abnormal assessments that are associated with the disease being studied, and are present at the start of the study but do not worsen, will not be reported as AEs or SAEs. However, if these findings or assessments are judged by the investigator to be more severe than expected considering the subject's condition, then they may be reported as AEs or SAEs.

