#### 11.4.2 Laboratory Data

Routine clinical laboratory results will be carried out at screening, all visits during the treatment period. The laboratory parameters include:

- Haematology: hemoglobin, hematocrit, WBC, neutrophils, lymphocytes, monocytes, eosinophils, basophils, platelet count, INR, PT
- Biochemistry: sodium, potassium, chloride, calcium, phosphate, glucose, BUN or urea, creatinine, AST, ALT, alkaline phosphatase, total bilirubin, GLDH, total protein, lipase, albumin, LDH, gGT, CRP,

Laboratory parameters will be summarised at each visit using descriptive statistics on the SAF set. Laboratory parameters classified as normal/ abnormal non clinically significant (NCS)/ abnormal clinically significant (CS) will be presented in a shift table showing changes from baseline to each visit for patients with at least one abnormal CS value. Baseline is defined as the last non-missing value before the first dose of study drug, which is Day 0.

If laboratory results are repeated at the same visit, the repeated result will be used in summaries (instead of the original one) provided the sample was taken within the visit window, otherwise the original result will be used. All results will be listed.

Laboratory results at unscheduled visits will be included in the listings but will not be summarised.

For all female patients of childbearing potential, a blood pregnancy test ( $\beta$ -HCG) will be performed at Day 0 and then a urine pregnancy test will be performed at each visit until VR. Results of all pregnancy testing will be listed only.

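### A DAIDS grade 3-4 laboratory value that the investigator calls not clinically significant can miss the DLT count, the grade-based AE tables and the SAP 11.4.2 shift table

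*Protocol*

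**What the plan says.** Three sets of rules meet on this point.

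- **DLT definition.** In the protocol synopsis, and again in SAP 3.1, a DLT is an adverse event of grade 3 or worse on the DAIDS table for the "severity of adult and pediatric adverse events (including signs/symptoms, lab toxicities and/or clinical events) considered by the Data Safety Monitoring Board" to be probably or definitely related. Protocol 3.1.2 gives the same definition but assigns causality to a safety review board. Two halts follow. One stops enrolment: "If more than 2 DLTs occur during the treatment period of the first four treated subjects". The other reads: "in case of a life threatening (grade 4) adverse reaction enrolment and treatment of ongoing subjects will be immediately discontinued".
- **AE recording.** Protocol 8.3.1 makes the investigator's view of clinical significance the test for laboratory findings and other abnormal assessments. Those that pass it "will be recorded as AEs or SAEs if they meet the definitions of sections 8.1 and 8.2 respectively". Protocol 5.4.3 says who decides: "The investigator will be responsible for assessing the clinical significance of laboratory abnormalities". The recording list in protocol 8.5 likewise asks for severity only of laboratory values that are clinically significant. Protocol 8.1 is wider: an abnormal laboratory finding can be an AE, with no significance test.
- **Reporting.** The synopsis leaves PCSA status to the investigator: "focusing on the detection of abnormal values and PCSAs [potentially clinically significant abnormalities (PCSAs) determined upon investigator" considerations. In SAP 11.4.2, "Laboratory parameters classified as normal/ abnormal non clinically significant (NCS)/ abnormal clinically significant (CS) will be presented in a shift table", but only for patients with at least one clinically significant (CS) value, and results from unscheduled visits are listed without being summarised. SAP 4.4 and protocol 9.3 count subjects with any abnormal value, and protocol 9.3.1 plans shift tables. None of these three carries a CS filter.

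**The concern.** The DLT criterion is a published grading table, and causality is reserved to a board. Under the recording rule, a laboratory value reaches that table and that board as an AE only after a prior judgement by the investigator at a single open-label site. If the value is marked not clinically significant (NCS), nothing in the documents says that it is graded, recorded as an AE or put before the board.

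Two things are at stake. The first is the input to the enrolment halt. The second is the secondary endpoint on number and grade of treatment-emergent AEs, which would under-report laboratory toxicity to the extent that grade 3-4 values are called NCS.

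**Working it through.** The plan gives no operating characteristic for the halt rule and no sample-size calculation, so there is no figure of its own to reproduce. The check is mainly a trace through the text.

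**Step 1: follow one value.** Take a grade 3-4 laboratory result, worse than baseline, that the investigator calls NCS.

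| Place | Does it appear? |
|---|---|
| AE record (protocol 8.3.1, 5.4.3) | Not required; protocol 8.1 would allow it |
| DLT count (synopsis, protocol 3.1.2, SAP 3.1) | No, unless it has become an AE |
| Grade 3+ AE tables (protocol 9.3, SAP 11.4.1) | No, for the same reason |
| Shift table in SAP 11.4.2 | No, unless the patient also has a CS value |
| By-visit minimum and maximum (SAP 10.1, 11.4.2) | Yes if scheduled, without its grade |
| Any-abnormal counts (protocol 9.3, SAP 4.4) | Yes if scheduled, without its grade |
| Shift tables in protocol 9.3.1 | No CS filter is stated |
| Unscheduled result (SAP 11.4.2) | Listing only |

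No laboratory table by DAIDS grade is planned. An any-abnormal count mixes trivial with severe values, and a maximum does not count subjects.

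**Step 2: the first four subjects.** Enrolment starts with Cohort 1 (protocol 6.4). Protocol 5.3 gives that cohort no scheduled visit between Day 1 and Day 28, because the Day 7, 14 and 21 visits are for Cohort 2. A Cohort 1 laboratory value taken in that interval, outside the Day 28 window, is unscheduled and so falls in the last row of the table.

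**Step 3: illustration of size.** Both inputs are assumptions; the documents give neither. Let p be the true DLT probability per subject (at most one each) and c the share of DLTs that reach AE status. More than 2 of 4 means 3 or 4, so with r = p × c:

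P(halt) = 4r³(1 − r) + r⁴

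| p | c = 1 | c = 0.75 | c = 0.50 |
|---|---|---|---|
| 0.25 | 0.051 | 0.023 | 0.007 |
| 0.50 | 0.313 | 0.152 | 0.051 |
| 0.75 | 0.738 | 0.412 | 0.152 |

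For example, p = 0.50 and c = 0.75 give r = 0.375, and 4(0.375)³(0.625) + (0.375)⁴ = 0.132 + 0.020 = 0.152.

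Seen another way, suppose that exactly three of the four subjects have a laboratory DLT and each is called NCS independently with probability q. All three are counted with probability (1 − q)³: 0.73, 0.51 and 0.34 at q = 0.1, 0.2 and 0.3.

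For the grade 4 rule over 12 subjects, with an assumed 10% rate, the chance of at least one recorded event is 1 − 0.90¹² = 0.718 if all are captured, and 1 − 0.95¹² = 0.460 if half are.

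In the tables, one missed subject is 1/12 = 8.3 percentage points of a cohort.

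**The case against.** The case on the other side has real substance.

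- **The value is not invisible.** A reader might infer that a grade 3-4 value called NCS drops out of every summary table. The documents do not support that. Scheduled values enter the by-visit descriptive statistics and the any-abnormal counts, and protocol 9.3.1 has unrestricted shift tables. This stands and limits the point to grade-based outputs, the SAP 11.4.2 shift table and unscheduled results.
- **The wording is ambiguous.** Protocol 8.3.1 does not say that only significant findings are AEs, protocol 8.1 is broader, and the DLT definition names laboratory toxicities outright. One can read it as reaching graded values directly. This stands too: the gap is an unresolved conflict, not a proven exclusion.
- **Liver tests have a numeric criterion.** Protocol 7.2 lists AST, ALT, alkaline phosphatase or total bilirubin at or above 2.0 × ULN as a treatment discontinuation criterion, with no significance call. A symptom-free transaminase rise is therefore a poor example. But the criterion does not say that the value is graded for the board, and other parameters in Table 4, such as lipase, neutrophils, platelets and creatinine, have none.
- **The board may see laboratory data.** It reviews safety every four patients under a charter that is not among these documents, so it cannot be claimed that the board would be unaware. Equally, nothing here says that it receives graded values, and SAP 7 plans no safety monitoring reports.
- **Bias by dose.** A reader might infer that calls would differ by dose because dose is known. Open-label conduct allows this, but nothing in the documents shows it. The cohorts are sequential and not randomised, and no formal safety comparison between doses is planned.
- **Timing.** SAP 8 reports the Cohort 1 interim as done. If the first four means the first four in the study, that halt window has passed. The grade 4 rule and the reporting gap remain.

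**Conclusion.** The concern holds in limited form. The DLT is built on adverse events and includes laboratory toxicities. Laboratory AEs are recorded on the investigator's call of significance, and no section overrides that call by DAIDS grade. A grade 3-4 value called NCS can therefore miss the DLT count, the grade-based AE tables and the SAP 11.4.2 shift table. If scheduled, it remains visible without its grade; if unscheduled, it is only listed.

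The size cannot be read from the plan. The probabilities above show how sensitive a three-of-four rule is to lost events. They rest on assumed p, c and q, on independence and on one DLT per subject, and are not properties of this trial. The reporting gap needs no such assumption and is cheap to close.

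**What to change.** 1. **SAP 11.4.2 and protocol 9.3.** Derive the DAIDS v2.0 grade by program for every gradable laboratory result, including unscheduled ones. Tabulate worst post-baseline grade, and the shift from baseline to worst grade, by cohort for all treated subjects. Keep NCS/CS as a descriptor. Reconcile SAP 11.4.2 with SAP 4.4 and protocol 9.3.1 on who enters the shift table. Protocol 5.4.3 already requires all results and reference ranges in the eCRF, so the cost is a small amount of programming and no new samples.
2. **Reconcile the passages.** The DLT definition (synopsis, protocol 3.1.2, SAP 3.1) must be reconciled with protocol 8.1, 8.3.1 and 5.4.3 on whether a DAIDS grade 3 or higher value called NCS is an AE and reaches the board for DLT assessment. The grading scale needs the same treatment: protocol 8.5 opens with DAIDS but its recording list uses CTC AE, and SAP 11.4.1 uses CTC for severe events while SAP 4.4 uses DAIDS. Because the answer feeds a rule that can stop treatment, the choice belongs to the sponsor and the board; no clinical or stopping rule is proposed here. The cost is clarifying text in both documents.
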